**A. Title** Preliminary evaluations of the accuracy, usability, and function of an automatic blood pressure monitor for use in the diagnosis and management of pre-eclampsia in low-resource hospitals

**D. Executive Summary**

Pre-eclampsia and eclampsia pose a significant threat to the health of mothers globally. The WHO estimates that 50,000 women worldwide die annually as a result of pre-eclampsia or eclampsia [1], with the majority in developing countries. The research team at Rice University has developed Sphygmo, an automatic blood pressure monitor to be used for the monitoring and diagnosis of pre-eclampsia in pregnant women, particularly in low-resource settings where current blood pressure monitoring is limited. This study aims to evaluate the clinical monitoring and diagnostic capabilities of the device in the setting for which it was designed - a low-resource hospital.

This is a **3- phase clinical community trial**. The first two phases are being completed by Rice University in Houston Texas. In phase 1, we will test the blood pressure monitor on healthy women followed by a secondary phase to test the monitor on pregnant women. Phase 3, in Malawi, the study will compare the Sphygmo device to a commercially available automatic blood pressure monitor that has been previously validated for accuracy in pre-eclamptic women and clinical auscultatory measurements taken by observers using a stethoscope and aneroid gauge [2, 3]. The main objective of this study is to determine whether the Sphygmo device correctly identifies instances where systolic and diastolic blood pressures meet the diagnostic criteria for mild or severe pre-eclampsia during monitoring of at-risk mothers.

Additionally, this study aims to understand the occurrence and type of any complications associated with the usability and function of Sphygmo in a resource-limited clinical setting.

The study will include 20 eligible and consenting women at QECH who are clinically identified as at-risk for pre-eclampsia or have already been diagnosed with pre-eclampsia. All participants will undergo the same protocol (monitoring with Sphygmo, the commercially available device, and using the auscultatory method). First, a nurse will fit a Sphygmo device cuff on one arm of the subject and the commercial cuff on the opposite arm. The nurse will program identical alarm thresholds and measurement intervals on the new device. A trained research assistant will be continuously on hand to assist the nurse in the device setup and record the blood pressure measurements and any alarm indications made by each device. Blood pressure measurements by Sphygmo and the commercial device will continue until monitoring is no longer clinically prescribed. All clinical decisions will be made according to the commercial device measurements. In addition, every hour an observer will take a blood pressure reading using the clinical auscultatory method to confirm that the readings of both the commercial device and Sphygmo are accurate.

The key results of the study will be the sensitivity and specificity of the Sphygmo device for identifying blood pressure levels corresponding to mild and severe pre-eclampsia. Additionally, a complication rate will be determined in regards to any user errors or device malfunction. These results will provide information on the performance, use, and usability of the device in its intended setting; this information will also alert the research team of any necessary design modifications for the device. The results of the study will be submitted for publication in a relevant research journal, such as the *American Journal of Obstetrics and Gynecology*.

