#### v. Sample Size

The Malawi study is a pilot study that is designed to provide data to be able to calculate the number of patients that would be needed in a full clinical trial to evaluate the efficacy of Sphygmo in diagnosing pre-eclampsia. As such, a sample of 10 participants would indicate how large of a sample would be required for the subsequent clinical trial. The sample size of 10 was suggested by collaborating clinical partners and feedback from statisticians. However, due to some patients potentially choosing to end study participation, the study team (researchers and clinical partners) will require a sample size of 20 to ensure the appropriate amount of data is collected.

The inclusion criteria for the clinical study in Malawi:

- Women who have been identified as at-risk for pre-eclampsia or have been diagnosed with pre-eclampsia during a visit to QECH.
- Women who have been clinically identified to benefit from continuous blood pressure monitoring.
- Women ages 18 or older.

The exclusion criteria for the clinical study in Malawi are as follows:

- Pregnant women who have already developed eclampsia.
- Women under age 18.

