## vi. Data Collection

Data will be collected on paper forms (Appendix 2) as is consistent with current clinical practice. Clinical and/or research personnel will record information, excluding personal identifiers, on a standardized patient monitoring form. After the patient's participation is completed, the research coordinator will collect and scan the form.

The following data points will be collected/processed:

- Patient history variables:
  - *Age*
  - *Gravidity*
  - *Estimated gestational age (or hours since delivery)*
  - *Mode of admission to hospital*
  - *Number of previous antenatal care visits*
- Threshold Accuracy:
  - *True positive (TP): Control device and Sphygmo cross alarm threshold*
  - *True negative (TN): Control device and Sphygmo do not cross alarm threshold*
  - *False positive (FP): Control device does not cross alarm threshold but Sphygmo does*
  - *False negative (FN): Control device crosses alarm threshold but Sphygmo does not*
  - *Sensitivity: TP/(TP+FN) with confidence intervals*
  - *Specificity: TN/(TN+FP) with confidence intervals*
- Usability:
  - *User error: dichotomous variable indicating incidence of nurse error (max 1 per device interaction)*
  - *Total number of Sphygmo device interactions by nurse*
  - *Percent of error-free device interactions by nurses*
- Device Function:
  - *Device malfunction: dichotomous variable indicating incidence of device malfunction (max 1 per device use)*
  - *Total number of device uses*
  - *Percent of malfunction-free device uses*

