## Blood Pressure Measurements

Measurement #	Time	Control Systolic / Diastolic (mmHg)	Test Device Systolic / Diastolic (mmHg)
1			
2			
3			
4			
5			
6			
7			
8			
9			
10			
11			
12			
13			
14			
15			
16			
17			
18			
19			
20			
21			
22			
23			
24			
25			
26			
27			
28			
29			
30			
31			
32			
33			
34			
35			
36			
37			
38			
39			
40			
41			
42			
43			
44			
45			

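### No rule says which arm takes the Sphygmo cuff, so a placement habit combined with an average inter-arm difference would be scored as device error

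*Combined protocol and SAP*

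**What the plan says.** The Executive Summary (section D) holds the only visible text on cuff placement: "a nurse will fit a Sphygmo device cuff on one arm of the subject and the commercial cuff on the opposite arm". No assignment rule, swap during monitoring or baseline reading in both arms is described there or in section H. The same section sets identical alarm thresholds for the two devices and states that "The key results of the study will be the sensitivity and specificity of the Sphygmo device" for blood pressure levels matching mild and severe pre-eclampsia.

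Section H.vi takes the control device as the truth. A false negative, for example, is a case where "Control device crosses alarm threshold but Sphygmo does not"; the other three cells are defined in the same way. Section H.vii lists means, sensitivity and specificity, rates and proportions, with no adjustment for arm. The visible form tables identify the device but not the arm.

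Section H.v says the pilot is "designed to provide data to be able to calculate the number of patients that would be needed in a full clinical trial". It wants 10 women and plans for 20, "due to some patients potentially choosing to end study participation".

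**The concern.** Device and arm are paired within each woman, and the analysis treats the whole difference between the two readings as Sphygmo error. Two conditions turn that into a directional bias: Sphygmo goes on one side more often than the other, and the arms differ on average in the enrolled women. The documents neither show nor prevent either condition. If both hold, a device with no bias of its own looks less sensitive and more specific than it is, or the reverse. Because the alarm thresholds are identical, nothing absorbs the offset.

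If Sphygmo is always on the same side, the control comparison cannot separate arm from device afterwards, so the rule has to be set before enrolment. The confidence intervals planned in section H.vi would not reveal the problem, because they describe sampling error around a shifted value. The shifted estimate would then go into planning the full trial.

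**Working it through.** The plan states no inter-arm difference, expected sensitivity or threshold value, so there is no figure of its own to reproduce. What follows is a sensitivity analysis on assumed inputs.

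**Closed-form check of the mechanism.** Let control = B + e1 and Sphygmo = B + d + e2, with no device bias, where d is Sphygmo's arm minus the control's arm. Assume SD(B) = 20, SD(e) = 5 and the threshold at the mean. At d = 0 the correlation is 400/425 = 0.941, and sensitivity = specificity = 1/2 + arcsin(0.941)/π = 0.890. At d = -5 they become 0.770 and 0.961; at d = +5, 0.961 and 0.770. The two measures move in opposite directions, as claimed. Across SD(B) of 10 or 20 and SD(e) of 3 or 5, d = -5 lowers sensitivity by 12 to 26 points.

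**Main model.** Assumptions: women's means N(145, SD 15), within-woman SD 10, 20 readings each, independent error SD 5 mmHg in each device, and an inter-arm difference that is constant within a woman and distributed N(μ, SD 5). The cut-offs of 140 and 160 mmHg are illustrative and not taken from the protocol. Scoring is per reading on a single pressure. Large-sample sensitivity with Sphygmo always on the same side:

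| μ (mmHg) | Cut-off 140 | Cut-off 160 |
|---|---|---|
| 0 | 88.1% | 76.8% |
| -1 | 86.2% | 73.8% |
| -2 | 84.2% | 70.6% |
| -3 | 82.2% | 67.3% |
| +3 | 92.6% | 84.5% |

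The loss at -3 is 88.1 - 82.2 = 5.9 points and 76.8 - 67.3 = 9.5 points. Specificity goes from 82.6% and 92.8% at μ = 0 to 88.9% and 95.6% at -3, or to 74.7% and 88.7% at +3. With device error SD 3 or 8, the loss in sensitivity at -3 is 6.2 or 5.6 points (140) and 10.3 or 8.3 points (160).

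**Partial habit.** With Sphygmo on the lower arm in 80% of women and μ = -3, the expected shift is 0.8 × (-3) + 0.2 × (+3) = -1.8 mmHg. Sensitivity is then 84.2% and 70.7%, against 87.4% and 75.9% when the sides are balanced.

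**Against sampling error.** With 20 women and μ = 0, the 95% range of observed sensitivity is about 79-94% (140) and 58-90% (160), wider than any loss above.

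**What balancing achieves.** Mean shift over 20 women, difference N(-3, 5):

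- Always the same side: -3 ± 1.96 × 5/√20, that is -5.2 to -0.8 mmHg.
- Exact 10:10 split: SD 5/√20 = 1.12, range ±2.2 around zero.
- Simple randomisation: SD √((25 + 9)/20) = 1.30, range ±2.6 around zero.
- 10:10 split, then a random 10 of the 20 remain: variance 25/10 + 9 × (1/10)(10/19) = 2.97, SD 1.72, range ±3.4 around zero.

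The gain is the removal of the -3 centre. The exact split adds little over simple randomisation.

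**Adjusting the device difference for arm.** The SD of a woman's mean difference is √(25 + 50/20) = 5.24 mmHg. With a true device difference of 0, an arm effect of 3 mmHg and Sphygmo on the lower arm in 16 of 20 women, the unadjusted estimate is (16 × (-3) + 4 × 3)/20 = -1.8. The arm-adjusted estimate, the average of the two side-specific means, is 0.0 with 95% half-width 1.96 × (5.24/2) × √(1/16 + 1/4) = 2.9. At 10 of 20 the half-width is 2.3. At 20 of 20 the estimate is -3.0 and cannot be adjusted.

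**The case against.** The strongest reply is that the harm is doubly hypothetical. It needs both a side preference and a non-zero average arm difference, and with weaker inputs it is small: at μ = -1 with an 80% habit, sensitivity is 86.9% and 75.0%, a loss of 1 to 2 points. Direction and size are indeed unknown, so this stands as a limit on the weight of the point. It does not supply a rule.

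Sampling error also matters more for planning. Taking p(1 - p) as a proxy for a precision-based sample size, the full -3 shift changes it by (0.822 × 0.178)/(0.881 × 0.119) = 1.4-fold, while the no-shift sampling range changes it by (0.79 × 0.21)/(0.94 × 0.06) = 2.9-fold. That is right, but the planned intervals display sampling error and do not display a placement bias.

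The unit of scoring is not fixed in section H.vi. Scored per woman (any crossing in 20 readings), the -3 shift takes sensitivity from 97.4 to 95.3% and from 89.1 to 82.4%, a smaller loss than per reading, although specificity moves more.

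The hourly auscultatory reading might expose a persistent one-sided discrepancy. Its arm is not stated, however, and it plays no part in the accuracy definitions, so as written it cannot separate arm from device. Finally, some appendix pages were not available to this review and may hold an arm field.

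**Conclusion.** The concern holds in its conditional form. Nothing in the visible plan stops a one-sided placement habit from appearing as device error in the key results. Under the stated assumptions, a consistent 1 to 3 mmHg arm difference moves sensitivity by roughly 2 to 10 points in either direction, with specificity moving the other way; a partial habit does proportionately less. These sizes rest wholly on assumed inputs and on a one-pressure, per-reading model, whereas the primary objective concerns systolic and diastolic criteria. The effect would be hard to see among 20 women. It matters as a bias carried into the next trial's planning figures, and it is worth correcting mainly because the correction is so cheap.

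**What to change.** Assign Sphygmo's arm by alternating enrolment number or from a blocked random list. Simple randomisation would do nearly as well. Record the arm actually used for each device and for each auscultatory reading, unless a form page not seen here already does so. Report the mean Sphygmo-minus-control difference adjusted for arm, with woman as a random effect, alongside sensitivity and specificity.

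Give sensitivity and specificity by arm as description only: with about 10 women per side and a -3 mmHg shift, the 95% range of sensitivity at the higher cut-off is roughly 32-89%.

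State what balancing does not cure. Zero-mean inter-arm scatter still costs about 2 to 3 points in this model, chance imbalance remains, and withdrawals or unequal monitoring time can disturb the split, since "Blood pressure measurements by Sphygmo and the commercial device will continue until monitoring is no longer clinically prescribed".

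The cost is one protocol line, one form field and slightly more analysis. No extra women, readings or cuff changes are needed.

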#### **F. Justification**

Pregnancy-related hypertensive disorders cause 50,000 deaths annually, primarily in the developing world [1]. One major barrier to the diagnosis and management of pre-eclampsia is the time-intensive nature of conventional mercury sphygmomanometry, which is difficult in low-resource settings. There is a need for a blood pressure monitor that can independently monitor blood pressure and alarm if the pressure reaches the diagnostic criteria for mild or severe pre-eclampsia. This device must be shown to have a high level of accuracy and usability in low-resource settings.

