**Errors/Questions by Nurses**

Time	Nurse ID	Description of Error/Resolution

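### The percent of error-free nurse interactions describes use with an assistant helping at setup, and the plan does not separate unaided from assisted interactions

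*Combined protocol and SAP*

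**What the plan says.** In the Executive Summary (section D) the nurse fits the cuffs and enters the settings: "The nurse will program identical alarm thresholds and measurement intervals on the new device". The same paragraph adds: "A trained research assistant will be continuously on hand to assist the nurse in the device setup". Help with setup is thus an assigned duty of someone who is present throughout.

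Section H.vi (Data Collection, Usability) lists three items. The first is the yes/no variable, "User error: dichotomous variable indicating incidence of nurse error (max 1 per device interaction"). The second is the denominator, "Total number of Sphygmo device interactions by nurse". The third is the result, "Percent of error-free device interactions by nurses". There is no level for an interaction completed correctly with help, and the denominator is not divided into setup and other interactions.

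The Appendix 2 form has one table, "Errors/Questions by Nurses", with columns for time, nurse ID and "Description of Error/Resolution". Section F sets the wider aim: "This device must be shown to have a high level of accuracy and usability in low-resource settings".

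**The concern.** Usability is one of the two primary objectives in section G, and this percentage is the planned numeric result for use by nurses. Section D intends the results to describe usability in the intended setting and to point to design changes. Section I (Potential Benefits) describes very low resource settings as short of hospital staff, and no section says that a dedicated assistant would be there in routine use.

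If a nurse gets through setup only because the assistant spoke up in time, the interaction enters the numerator in the same way as one done alone. A reader of the published percentage could take it as unassisted performance. Logged questions can be classified afterwards from their time and description. Unprompted help that was never written down cannot be recovered, and it is just the information that a design team would want.

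**Working it through.** The documents give no expected error rate, target percentage or number of interactions for usability, so there is no stated figure to reproduce. The check has two parts.

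**Part 1: how each kind of interaction would be scored**, reading section H.vi beside the Appendix 2 table.

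1. The nurse does it correctly alone: no row, error-free.
2. The nurse takes a wrong step and it is put right: the column "Description of Error/Resolution" can hold this, and the natural score is an error.
3. The nurse asks first and then does it correctly: this can be logged as a question. Whether the row counts as an error is not stated in the text provided.
4. The assistant steps in unprompted before any wrong step: no row is required, and the interaction is error-free.

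Only case 4 can vanish from the record. Case 3 is recorded, but its effect on the percentage depends on an unstated rule.

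**Part 2: possible size.** From the documents: 20 women. Everything else is assumed: one setup per woman, *k* other Sphygmo interactions per woman (all error-free), a proportion *e* of setups that would go wrong without help, and a share *q* of those averted before any wrong step.

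If questions are not scored, the overstatement of the pooled figure is 100 × e × q / (1 + k) points.

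- e = 0.20, q = 0.50, k = 2: 100 × 0.10 / 3 = 3.3 points.
- e = 0.30, q = 0.75: 22.5 / (1 + k), which is 11.25 points at k = 1, 4.5 at k = 4 and 1.1 at k = 19. These are the top values for e from 0.10 to 0.30 and q from 0 to 0.75, and they need the highest assumptions together.
- q = 0: no overstatement at any k.

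Direction, for e = 0.20, q = 0.50, k = 2. There are 20 × 3 = 60 interactions, and 4 of 20 setups would fail unaided. Two of these are averted (1 unprompted, 1 after a logged question) and two become logged errors. The unassisted figure is 56/60 = 93.3%.

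- Questions not scored: 58/60 = 96.7% (+3.3 points).
- Every row of the table scored as an error: 57/60 = 95.0% (+1.7).
- The same, with 1 further non-essential question: 56/60 = 93.3% (0).
- The same, with 3 further non-essential questions: 54/60 = 90.0% (-3.3).

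For setup alone, the unassisted figure is 16/20 = 80%. The recorded figure is 18/20 = 90% if questions are not scored and 17/20 = 85% if the one logged question is. Each setup is worth 1/20 = 5 points.

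**The case against.** - **The plan does not promise an unassisted figure.** The objective in section G is descriptive, section D states openly that the assistant is present, and section F expresses a general need and not an endpoint of this pilot. This stands as far as it goes: the percentage is not wrong as a description of assisted use. But section D offers the results as usability in the intended setting, so readers need to know how much help lies behind the number.
- **The form already records errors that were corrected.** This stands. A reader might infer that every mistake the assistant catches disappears. The resolution column does not support that; the gap is confined to unprompted help before a wrong step, plus the unscored questions.
- **The direction is not fixed.** This stands. A reader might infer that the percentage is bound, or likely, to be too high. The documents do not support that without a scoring rule for questions, and nothing shows how often the assistant would intervene unprompted.
- **Not all help hides a Sphygmo error.** Setup involves two devices with matched settings, so some help may concern the commercial monitor or study procedure. This is fair, and is one reason why the size cannot be stated.
- **The form is only partly visible.** The patient-history items listed in section H.vi do not appear on the pages provided, so a field for assistance or a scoring note elsewhere cannot be excluded. The yes/no definition in section H.vi is visible and has no assisted level.
- **It is a pilot with no pass mark on usability.** This is true, and it limits the consequence to how the figure is read and what design information is kept.

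**Conclusion.** The point holds in a limited form. As defined, the percent error-free describes nurses working with a trained assistant who helps at setup, and it may overstate unassisted usability. The size cannot be found from the documents. Under the assumptions shown, with questions unscored, it runs from 0 to 11.25 points on the pooled figure and shrinks as interactions per woman increase; if questions are scored as errors, the figure can fall below the unassisted value. Accuracy results and clinical decisions are not affected. This is a cheap improvement to make before enrolment, because unlogged help cannot be reconstructed later.

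**What to change.** On the Appendix 2 form, have the assistant mark each Sphygmo interaction on two items:

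- setup or other;
- correct without help, correct with help (prompted or asked), or error (including errors that were corrected).

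State in section H.vi that a logged question counts as assisted and not as an error. Keep the planned percent error-free, described as obtained with an assistant present. Report beside it the percent completed correctly without assistance, for setup and other interactions separately.

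In the illustration this would give 58/60 = 96.7% error-free and 56/60 = 93.3% correct without help; for setup alone, 18/20 = 90% and 16/20 = 80%. Three further non-essential questions, each at an otherwise unaided and correct interaction, would leave the first pooled figure at 96.7% and lower the second to 53/60 = 88.3%. The second figure can therefore be conservative, and showing both makes the gap visible.

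The cost is a small recording burden for someone already present, a few lines of protocol text, and a second figure that is less favourable and, for setup, coarse (steps of 5 points if there are 20 setups).

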##### Specific:

- Primary Efficacy Objective: Determine whether the Sphygmo device correctly identifies instances where systolic and diastolic blood pressures meet the diagnostic criteria for mild or severe pre-eclampsia during monitoring of at-risk mothers.
- Primary Usability Objective: Understand the occurrence and type of any complications associated with the usability and function of Sphygmo in a resource-limited clinical setting.

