#### **H. Research Methodology/Materials and Methods**

##### i. Study Type

This is a **3- phase clinical community trial**. The first two phases are being completed by Rice University in Houston Texas. In phase 1, we will test the blood pressure monitor on healthy women followed by a secondary phase to test the monitor on pregnant women. Phase 3, in

Malawi, the study will compare the Sphygmo device to a commercially available automatic blood pressure monitor on women who are at-risk for pre-eclampsia or have already been diagnosed with pre-eclampsia.

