#### iii. Study Population

The study will include 20 women in Malawi who are clinically identified as at-risk for pre-eclampsia or have already been diagnosed with pre-eclampsia. These women will either be pregnant or up to 48 hours postpartum. All participants in the study will undergo the same protocol (monitoring with Sphygmo, the commercial device, and using the auscultatory method). All eligible and consenting women will be enrolled in the study if a Sphygmo device and the commercial monitor are available at the time of clinical need for blood pressure monitoring.

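### Hourly auscultation is a stated comparator in Malawi, but no data item or analysis uses it, so accuracy is measured only as agreement with the control monitor

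*Combined protocol and SAP*

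**What the plan says.** The Executive Summary (section D) sets two comparators for the Malawi phase: a commercial monitor "previously validated for accuracy in pre-eclamptic women and clinical auscultatory measurements taken by observers using a stethoscope and aneroid gauge". It adds that "every hour an observer will take a blood pressure reading using the clinical auscultatory method to confirm that the readings of both" the commercial monitor and Sphygmo are accurate. Section H.iii applies this to every woman: "All participants in the study will undergo the same protocol (monitoring with Sphygmo, the commercial device, and using the auscultatory method".

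The operational sections do not follow through:

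- **Recording (section D).** The research assistant is to "record the blood pressure measurements and any alarm indications made by each device". The natural reading is device readings and device alarms.
- **Study type (H.i).** Here "the study will compare the Sphygmo device to a commercially available automatic blood pressure monitor on women who are at-risk for pre-eclampsia" or already diagnosed. Auscultation is not mentioned.
- **Data items (H.vi).** No auscultatory value is listed. True and false positives and negatives, and hence sensitivity and specificity, are all defined against the control device.
- **Analysis (H.vii).** It promises accuracy in general terms, presented as means, sensitivity and specificity, rates and proportions. No auscultatory comparison is specified.

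The measurement table on the data form has columns for control and test device only. Other form pages may be missing from the reviewed text, so the point does not rest on the form.

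**The concern.** The primary efficacy objective (section G) is to "Determine whether the Sphygmo device correctly identifies instances where systolic and diastolic blood pressures meet the diagnostic criteria" for mild or severe pre-eclampsia. The measures in H.vi answer a narrower question: does Sphygmo alarm when the control monitor alarms?

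Two things follow. Where the control is wrong and Sphygmo is right, Sphygmo is charged with a false positive or a false negative. Where both automatic devices err in the same direction, they agree, and nothing specified for Malawi reveals it. The hourly auscultatory reading is the one planned measurement that could separate a Sphygmo-only difference from a difference common to both devices.

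This matters beyond the pilot, which is "designed to provide data to be able to calculate the number of patients that would be needed in a full clinical trial" (H.v). Accuracy estimates carried into that calculation would inherit the same limitation.

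**Working it through.** **Step 1: the text.** The documents state no figure that tests this point, so the check is whether each section gives auscultation a role.

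| Section | Role of auscultation |
|---|---|
| D, Executive Summary | Comparator; hourly; to confirm both devices |
| H.iii Study Population | Done in all participants |
| H.i Study Type | None |
| H.vi Data Collection | No data item; reference is the control device |
| H.vii Analysis | None specified |

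The stated purpose therefore has no data item and no analysis behind it.

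**Step 2: what control-based scoring can hide (all inputs assumed).** True pressure is normal with SD 15 mmHg; figures come from bivariate-normal integration.

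- *Case A:* Sphygmo is error-free and the control has random error SD 5.
- *Case B:* both devices under-read by 5 mmHg, with independent random error SD 3 each. Sphygmo minus control then averages 0.

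| Mean pressure relative to cut-off (mmHg) | A: sensitivity vs control | B: sensitivity vs control | B: true sensitivity |
|---|---|---|---|
| −20 | 0.73 | 0.77 | 0.55 |
| −10 | 0.82 | 0.83 | 0.64 |
| 0 | 0.90 | 0.89 | 0.74 |
| +10 | 0.95 | 0.93 | 0.84 |
| +20 | 0.98 | 0.97 | 0.92 |

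In case A with the mean on the cut-off, specificity is also 0.90, although Sphygmo makes no error. In case B the gap shrinks as mean pressure rises (from 0.22 to 0.05) but does not close.

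**Step 3: what the hourly readings could show.**

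Inputs:
- Women: n = 10 or 20 (H.v).
- Hourly points per woman, k: the form has 45 rows. At an assumed 15- or 30-minute interval these cover 45 × 0.25 = 11.25 or 45 × 0.5 = 22.5 hours, so k = 11 or 22. For a short stay, k = 4 is assumed.
- SD of device minus auscultation (assumed): between women sb = 3 or 5 mmHg, within woman sw = 5 mmHg.

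Standard error of the mean difference: SE = √(sb²/n + sw²/(n·k)). The 95% half-width is t(0.975, n−1) × SE.

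- n = 20, smallest: 2.093 × √(9/20 + 25/440) = 2.093 × 0.712 = 1.49 mmHg.
- n = 20, largest: 2.093 × √(25/20 + 25/80) = 2.093 × 1.250 = 2.62 mmHg.
- n = 10, smallest: 2.262 × √(9/10 + 25/220) = 2.262 × 1.007 = 2.28 mmHg.
- n = 10, largest: 2.262 × √(25/10 + 25/40) = 2.262 × 1.768 = 4.00 mmHg.

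Chance that the 95% interval excludes zero (noncentral t, same SE):

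| True mean difference | 20 women | 10 women |
|---|---|---|
| 3 mmHg | 0.62–0.98 | 0.33–0.76 |
| 5 mmHg | 0.97–1.00 | 0.71–0.99 |
| 8 mmHg | about 1.00 | 0.98–1.00 |

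Limits of agreement lie at the mean difference ± 1.96 × √(sb² + sw²): ± 1.96 × √34 = ± 11.4 or ± 1.96 × √50 = ± 13.9 mmHg. By simulation (20,000 trials per setting), each limit is known to about ± 1.8–3.8 mmHg with 20 women and ± 2.6–5.4 with 10.

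**Step 4: auscultation's own error.** The observed difference is device bias minus auscultation bias. If auscultation is off by −3 to +3 mmHg, a shared under-read of 5 appears as −5 + 3 = −2 to −5 − 3 = −8, and unbiased devices appear as +3 to −3.

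**The case against.** The control monitor is a legitimate reference. The protocol describes it as validated in pre-eclamptic women and FDA-approved, and it guides all clinical decisions. Scoring a new device against such a monitor is normal in a pilot, and any such study measures agreement. This stands, and the control-based result should stay as the main one.

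Auscultation could also be only a bedside check, and the recording instruction could be read to include it. Either reading is possible. But the Executive Summary calls it a comparison and gives no criterion for what counts as confirmed. Even if the values are written down, H.vi and H.vii give them no use.

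The numerical inputs are assumed. The between-woman SD may be too small, because "First, a nurse will fit a Sphygmo device cuff on one arm of the subject and the commercial cuff on the opposite arm", which brings in an inter-arm difference. With an SD of 8 and four points per woman, the half-width rises to 2.093 × √(64/20 + 25/80) = 3.9 mmHg with 20 women, or 2.262 × √(64/10 + 25/40) = 6.0 with 10. Nothing in the documents suggests that the control under-reads by 5 mmHg. These objections limit the size of the effect, not the finding.

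Finally, an added table leaves the threshold measures as they are and cannot by itself settle which instrument is wrong. That is true. It can only show whether Sphygmo alone departs from auscultation or both devices do.

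**Conclusion.** The point holds. A comparator named in the Executive Summary and measured hourly in every woman has no listed data item and no specified analysis. Following H.vi and H.vii as written leaves the stated confirmation of accuracy undone, and sensitivity and specificity can be read only as agreement with the control.

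This should be corrected, but it does not invalidate the main result. The finding rests on the text alone. Its size cannot be derived from the documents. Under the assumptions shown, a shared 5 mmHg under-read leaves true sensitivity 0.05 to 0.22 below the control-based figure. The hourly readings would very probably show a mean difference of 5 mmHg with 20 women, but could miss 3 mmHg, mainly with 10, and both chances fall if the between-woman SD is nearer 8.

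**What to change.** - **H.vi and the form:** add the hourly auscultatory systolic and diastolic values, the time, and the arm used.
- **H.vii:** state that, at the hourly points, the mean difference, SD and limits of agreement against auscultation will be reported for both Sphygmo and the control, with intervals that allow for repeated readings within a woman.
- **Main result:** keep control-based sensitivity and specificity, described as agreement with the control device.
- **H.i:** name the same comparators as the Executive Summary. If no comparison with auscultation is intended, the Executive Summary should say so instead.
- **Interpretation:** state in advance that a difference shared by both devices is a signal to investigate, because auscultation has its own gauge and observer error.

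The cost is a few form fields and one table, with no new measurement. Hourly points are fewer than paired device readings (about 11 or 22 against 45 form rows per woman under the assumed intervals), so intervals are wider. With cuffs on opposite arms, a manual reading on one arm adds an inter-arm difference for at least one device, as well as a timing difference; recording arm and time lets the reader judge both.
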